Subjects meeting the following criteria

- Age older than 18 and younger than 75
- Recent (less than one month) development of exertional dyspnea

Exclusion Criteria

Subjects meeting the following criteria:

- Anticoagulation required for other indications
- Contraindication to CT angiography (allergy to the contrast dye, severe renal failure [creatinine clearance < 30 ml/min])
- Involvement in simultaneous clinical trials
- Unable to provide their written informed consent

Study Procedures

Enrolment Procedures

All eligible patients will be interviewed and examined by trained study physicians. The presence of already known potential explanations for the dyspnea (see before) will be assessed. In addition, symptoms of the lower extremities will be elicited, as well as the presence of risk factors for venous thromboembolism (VTE), including recent surgery, trauma or infectious disease, ongoing hormonal treatment, prolonged immobilization, active cancer and history of VTE. The severity of dyspnea will be classified according to the modified scale of the Medical Research Council.

The presence or absence of pulmonary embolism will be assessed with the use of a validated algorithm based on pre-test clinical probability and D-dimer result. The D-dimer level will be assessed with the quantitative assay routinely used in each participating center, and the cut-off will be adjusted to patients age in a standardized fashion. The pre-test clinical probability will be assessed by the simplified Wells score that classifies it as being “likely” or “unlikely”. In patients in whom the pre-test clinical probability is low (“unlikely”) and the D-dimer result is negative, no further testing will

be done, and PE will be considered excluded. In patients with high clinical probability, positive D-dimer result, or both, computed tomography (CT) pulmonary angiography will be performed. Criterion for the presence of PE will be an intraluminal filling defect on CT angiography. In patients with PE, the thrombotic burden will be assessed by a central adjudication committee through the identification of the most proximal location of the embolus on CT angiography.

Definition of the conclusion of the study

Stoplines:

- after enrolling 300 patients, if the lower limit of the 95% CI of the prevalence of PE is $\geq 20\%$;
- otherwise:
- after enrolling 600 patients

Outcome of the study

Primary endpoint

- Prevalence of PE in the overall population

Secondary endpoints:

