Prevalence of PE in the following subgroups:

- patients with high pre-test clinical probability and/or positive D-dimer
- patients without potential explanations for the dyspnea
- each of the 5 severity groups of the modified scale of the Medical Research Council

Statistical consideration

Bias

To avoid patient's selection bias, the investigators are asked to consecutively include the observed patients or, if it is not possible, to declare the criterion adopted for enrolment (e.g. one day a week, one week a month, etc.).

Sample size

Based on pilot data, we assume a prevalence of PE in patients with dyspnea on exertion between 10 and 15%. In order to obtain a two-sided 95% confidence interval (CI) of 2.5% for the prevalence of PE, we estimate that a sample size of 550 patients is required. All centers will be asked to contribute patients until the achievement of the overall sample size.

Statistical analysis plan

The prevalence of PE and the associated 95% CI will be calculated for the entire group of patients and for relevant subgroups. For comparison of baseline characteristics between patients with and without PE, the chi-square test will be used for categorical parameters, while the Student's t-test will be used for continuous parameters. Odds ratios and their 95% CIs will be calculated using logistic regression. The 95% CIs and P values will be calculated according to the normal approximation of the binomial distribution. No adjustments will be made for multiple testing.

An interim analysis will be performed after the inclusion of 300 patients. If the lower limit of the 95% CI around the prevalence of PE is $\geq 20\%$, the study will be interrupted.

Study administration

Data collection and management

Patient's personal data will be collected (in anonymous form), date of birth, gender, weight, height, liver and hepatic enzymes, past clinical history, thrombotic/haemorrhagic risk factors, lifestyle habits, type of treatment

The monitor of the study will check data quality and completeness by remote monitoring.

Data will be anonymously entered by the investigator in the eCRF, by assigning a patient identification code.

The adopted database is REDCap stored in the server owned by Fondazione Arianna Anticoagulazione, which is responsible for maintaining, and backing up the database..

Each access to the eCRF will be managed by personal user name and a password.

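### Does the stop at 300 patients for a high PE prevalence undermine the precision and validity of the primary estimate?

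*Combined protocol and SAP*

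**What the plan says.** The rule appears twice in the combined protocol and SAP, in the same terms. Under Definition of the conclusion of the study, the first stopline applies "after enrolling 300 patients, if the lower limit of the 95% CI of the prevalence of PE is" at least 20%; otherwise enrolment ends at 600. The Statistical analysis plan section repeats it: "An interim analysis will be performed after the inclusion of 300 patients", and "If the lower limit of the 95% CI around the prevalence of PE is" at least 20%, the study is interrupted.

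The Sample size section supplies the context: "we assume a prevalence of PE in patients with dyspnea on exertion between 10 and 15"%, a target of a "two-sided 95% confidence interval (CI) of 2.5% for the prevalence of PE", and 550 patients as the resulting size. On method, "The 95% CIs and P values will be calculated according to the normal approximation of the binomial distribution". The primary endpoint is the prevalence of PE in the overall population. The plan gives no reason for the 20% limit, does not state the precision expected after an early stop, and describes no estimate adjusted for the stopping rule.

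**The concern.** An early stop usually serves a test or protects participants. Here the primary aim is an estimate, no hypothesis about 20% is stated, and the study is observational. The rule therefore seems to give up precision for nothing the documents name. Four things appear to be at stake:

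- Under the plan's own 10–15% the rule can hardly ever act, which makes it look idle or misjudged.
- If it does act, the half-width is about ±5 points, roughly twice the figure the study was sized for.
- The stopped estimate is high by selection and would be reported with an ordinary CI.
- The secondary subgroups are halved. The five dyspnoea grades, for example, would average 60 patients instead of 120.

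A further worry is that an observed 25%, against an expected 10–15%, could reflect selective enrolment. Stopping would then fix a doubtful result in place.

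**Working it through.** **Inputs.** From Sample size: prevalence 10–15%, two-sided 95% CI (z = 1.96), target 2.5%, n = 550. From the Statistical analysis plan section: normal-approximation CI, look at n = 300, stop if the lower limit is at least 20%. From the stoplines: 600 patients otherwise. Patients are treated as independent.

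**1. The plan's own figure.** With n = z²p(1−p)/h², p = 0.10 and h = 0.025: 3.8415 × 0.09 / 0.000625 = 553.2, so 554, close to the stated 550. The 2.5% is therefore a half-width, and it fits the 10% end of the range only; p = 0.15 gives 784. With 600 patients the half-width is ±2.40 at 10% and ±2.86 at 15%.

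**2. The stopping boundary.** The rule needs the smallest x with x/300 − 1.96·√(p̂(1−p̂)/300) ≥ 0.20.
- x = 74: lower limit 0.1979, no stop.
- x = 75: 0.2500 − 0.0490 = 0.2010, stop.

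So at least 75/300 (25.0%) is needed. A Clopper–Pearson limit gives the same boundary; a Wilson limit gives 74.

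**3. Operating characteristics.** Exact binomial enumeration of the first 300 and, without a stop, the second 300:

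| True prevalence | P(stop) | Bias given a stop (points) | Bias over all paths (points) | Coverage given a stop | Coverage over all paths |
|---|---|---|---|---|---|
| 10% | 7.4 × 10⁻¹⁴ | +15.2 | 0.00 | 0% | 93.9% |
| 12.5% | 2.8 × 10⁻⁹ | +12.7 | 0.00 | 0% | 94.9% |
| 15% | 4.3 × 10⁻⁶ | +10.3 | 0.00 | 0% | 94.5% |
| 20% | 2.0% | +5.7 | +0.06 | 0% | 93.9% |
| 22% | 11.9% | +4.1 | +0.24 | 85.6% | 94.5% |
| 25% | 52.2% | +1.9 | +0.50 | 96.0% | 94.8% |
| 28% | 89.0% | +0.5 | +0.24 | 98.0% | 96.1% |
| 30% | 97.6% | +0.15 | +0.07 | 97.1% | 96.3% |

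The zeros for coverage given a stop at 20% and below hold by construction: a stop requires a lower limit of at least 20%, and the smallest one attainable is 20.1%.

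**4. Where the doubling comes from.** At the boundary the half-width is 1.96·√(0.25 × 0.75/300) = 4.90 points, and 4.90/2.5 = 1.96. This splits into two factors:
- fewer patients: √(550/300) = 1.35;
- higher prevalence: √(0.1875/0.09) = 1.44.

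At 25% prevalence, 600 patients would give ±3.46. The stop itself therefore costs 4.90/3.46 = 1.41-fold, or 4.90 − 3.46 = 1.44 points. At 30% the comparison is ±5.19 against ±3.67.

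**5. What removing the rule would buy.** On the path where the rule acts, 300 more patients narrow the half-width by about 1.5 points and still miss ±2.5. On every other path nothing changes.

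**6. What an adjusted estimate would buy.** For a stop at the first look, a median-unbiased estimate under stagewise ordering is essentially the ordinary one (25.0% for 75/300). Ordering by the estimate itself moves it only about half a point lower, to about 24.5%. Neither removes a conditional bias of 4 to 6 points at a true 20–22%.

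**The case for a change.** The strongest case for a change is that a pre-specified rule ought to serve the primary aim in the situation where it acts. This one acts only when prevalence is well above the planning range. It then returns a wider interval and, at a true prevalence of 20–25%, an estimate about 2 to 6 points too high on average among stopped studies. At a true 22%, the interval reported after a stop covers 86% of the time. The documents name no benefit that pays for this, and removing the rule would cost only recruitment already foreseen.

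The figures stand, and so does the absence of a stated reason for 20%. The inference is weaker.

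- The poor conditional results belong to unlikely stops (2% at a true 20%, 12% at 22%). Where stopping is likely, conditional coverage is nominal or better.
- A rule meant for a prevalence far above expectation should almost never act at 10–15%, so its rarity there is not a fault.
- The enrolment argument does not lead to more recruitment. If selection inflates the prevalence, another 300 patients recruited in the same way narrow the interval around the same wrong value. The Bias section already asks for consecutive inclusion or a declared enrolment criterion.
- The subgroups do lose patients, but the plan sets no precision target for them.

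**Conclusion.** No change is needed. The rule is stated in advance and identically in both places, and it is inert under the assumed 10–15% (probability of stopping at most 4.3 × 10⁻⁶). If prevalence is much higher, the study as planned still gives a sound answer: bias over all paths of at most about 0.5 points, overall coverage of 94–96%, and a lower limit of at least 20% whenever it stops. The cost of a stop is a half-width of about ±4.9 to ±5.2 points for a prevalence of 25–30%, where 600 patients would give ±3.5 to ±3.7. The sponsor may reasonably accept that to save 300 patients. Deleting the rule would be a different design choice, not the correction of an error.

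The planned 2.5% is tied to the 10–15% assumption and makes no promise about 25%. The precision after a stop needs no separate statement to be known, since the reported CI will show it.

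The conclusion assumes independent patients. Clustering by centre, which the documents do not quantify, would raise the stopping probabilities somewhat. It also takes the 10–15% at face value. Near a true 20–22%, a stopped result should be read knowing that the rule selects high values.

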Pulmonary embolism (PE) is an insidious disease, frequently not recognized or mistaken for other pathologies, and is accompanied by a high mortality rate if not properly identified and treated (1). The onset modalities that often lead to erroneous diagnostic conclusions include angina-type chest pain, right or congestive heart failure, the exacerbation of chronic obstructive pulmonary disease, pneumonic pulmonary thickening, pleuritic pleural effusion and syncope (2). Recently it has been shown that the application of an adequate diagnostic algorithm can allow the recognition of PE in over 17% of patients hospitalized for a syncopal episode (3). In the PIOPED II study, 16% of patients with documented PE had come to the observation for exertional dyspnea, that is, a shortness of breath for physical activities that usually do not determine it (4). The most common cause is congestive heart failure. Other conditions that can cause it are chronic obstructive pulmonary disease, lung disease (e.g. pneumonia), aortic stenosis, severe anemia, hyperthyroidism, lung cancer, liver and kidney disease and psychopathological disorders. Although PE has been identified among the conditions that can cause exertional dyspnea (4), it is rarely suspected and its prevalence in subjects who reach the Emergency Departments for this condition is unknown.

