The international guidelines for the diagnostic approach to patients with suspected EP recommend the use of a clinical probability score in combination with the result of a laboratory test, the D-Dimer (2). The most commonly used stratification model is the one described by Wells and associates, which scores a number of partly anamnestic and partly clinical parameters, and allows to identify as having a high pre-test clinical probability those subjects who score at least 4 (5). Based on the results of several clinical studies, patients with both a low clinical probability and negative D-Dimer can be regarded as not having PE (2). Accordingly, these patients do not require further diagnostic tests. In order to reduce the risk of false positivity D-Dimer tests (test of high sensitivity to thromboembolism, but of poor specificity), an algorithm that takes into account the patient's age has been successfully tested in subsequent studies of wide international impact. More specifically, it has been shown that with the adoption of sensitive D-dimer tests (cutoff 500 ng/ml) it is safe to withhold pulmonary CT angiography from patients older than 50 years whose laboratory test does not exceed a value that is achieved by multiplying their age by 10 (6).

General Aims and Study Objectives

This observational, cross-sectional, multicenter Italian study aims at investigating the prevalence of PE in a consecutive series of patients who refer to the Emergency Departments (either spontaneously or sent by their attending physicians) for the recent (less than one months) development of exertional dyspnea.

Objectives

To assess the prevalence of PE (and its 95% CI) in the overall population as well as in relevant subgroups (patients who will be imaged, patients without potential explanations for dyspnea).

Investigational Plan

Study design

The PEDIS study is an observational study, national multicenter and no Profit.

Setting

Emergency departments

Timeline

Data planned for the study beginning (first patient enrollment): 1 July 2018

Data planned for the last patient enrollment: 1 September 2019 or the achievement of the target of 600 patients.

Study population

All consecutive patients who refer to the Emergency Departments of the participating centers will be eligible for the study provided they are older than 18 and younger than 75 years, and have developed one or more episodes of exertional dyspnea since less than one month.

Inclusion Criteria

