The security system requires that the password be changed at the first access; it requires a length of at least 8 characters and provides for a periodic 3-month expiry.

It is obviously possible to disable the login, if it is deemed necessary by the system administrator.

Investigators can have full access only to their patient's data.

Every night the data backup is automatically performed.

Ethics

The study will be conducted in accordance with the ethical principles that have their origin in the Declaration of Helsinki and in compliance with the protocol and ICH-GCP.

This is an observational study and all drug prescriptions and clinical investigations are independent from the study.

The protocol and any amendments and the informed consent form (or information/non-opposition letter, as allowed by local regulations) will have to obtain Institutional Review Board or Ethics committee (IRB/EC) approval prior to initiation of the study.

Informed Consent Form

Participation in this study is entirely voluntary. Informed consent will be obtained in accordance with the Declaration of Helsinki, ICH GCP and local regulations. A properly executed, written, informed consent will be obtained from each subject prior to entering the subject into the trial. Information should be given in both oral and written form and subjects (or their legal representatives) must be given ample opportunity to inquire about details of the study. If appropriate and required by the local IRB/IEC, assent from the subject will also be obtained. If a subject is unable to sign the informed consent form (ICF) a legal representative may sign for the subject. A copy of the signed consent form will be given to the subject or legal representative of the subject and the original will be maintained with the subject's records. Once a patient has been enrolled in the study, he/she may withdraw his/her consent to participate in the study at any time without prejudice. Patients will not be entered in the database if the informed consent has not been obtained.

Procedures implemented to guarantee data confidentiality

The investigators collected patient's personal data in anonymous form by assigning a patient identification code.

The adopted database is RedCap. Data anonymously entered in the eCRF will be recorded and stored in the server owned by Fondazione Arianna Anticoagulazione. Each access to the eCRF will be managed by personal user name and a password.

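### Does calling all investigations independent of the study undermine the Wells/D-dimer/CT work-up that defines the primary endpoint?

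*Combined protocol and SAP*

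**What the plan says.** The Ethics section describes the study as observational and states that "all drug prescriptions and clinical investigations are independent from the study". The sentence before it says the study will be run "in compliance with the protocol and ICH-GCP".

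Under Study Procedures, the presence or absence of PE "will be assessed with the use of a validated algorithm based on pre-test clinical probability and D-dimer result". A patient with low clinical probability and a negative D-dimer is taken not to have PE and is not tested further. For all others, "computed tomography (CT) pulmonary angiography will be performed". The diagnostic standard is explicit: "Criterion for the presence of PE will be an intraluminal filling defect on CT angiography". The Exclusion Criteria include "Contraindication to CT angiography".

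The introduction says of PE in exertional dyspnoea that "it is rarely suspected and its prevalence in subjects who reach the Emergency Departments for this condition is unknown".

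The Objectives mention "relevant subgroups (patients who will be imaged, patients without potential explanations for dyspnea". The Secondary endpoints list defines the corresponding subgroup by indication instead: high pre-test probability, a positive D-dimer, or both. The Statistical analysis plan section gives the prevalence and its 95% CI for the whole group and for subgroups. It has no rule for a patient whose PE status cannot be determined.

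**The concern.** The Ethics sentence covers all investigations without exception, while Study Procedures directs a specific set of them, including contrast CT. The work-up cannot simply be assumed to be what these patients would have had anyway: the guideline cited in the introduction concerns suspected PE, and the same introduction says PE is seldom suspected here.

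Three things could be at stake:

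- An ethics committee reading one section would get a different picture from a reader of the other.
- If the Ethics sentence were taken literally and testing left to local practice, some enrolled patients could lack a PE status, and the plan does not say how they enter the denominator.
- The imaged subgroup and the subgroup indicated for imaging could then differ, giving two possible denominators for one secondary endpoint.

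**Working it through.** **The plan's own figure.** Sample size for one proportion by the normal approximation: n = 1.96² × p(1 − p) / h². With p = 0.10 and h = 0.025 as half-width, n = 3.8416 × 0.09 / 0.000625 = 553.2, rounded up to 554, close to the stated 550. The planned half-width is 1.96 × √(0.10 × 0.90 / 550) = 2.51 points, so the full width is about 5.0 points.

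**CTs the algorithm needs.** PE is recorded only from CT, so the number of CTs is at least the number of PE cases.

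- At 600 patients: 0.10 × 600 = 60 to 0.15 × 600 = 90.
- At 550 patients: 55 to 82.5.
- The floor is lower if enrolment closes on the planned date before 600.
- Negative CTs add to it. Assumed yields of 50%, 30% and 20% (not in the documents) would give 120–180, 200–300 and 300–450 CTs at 600.

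All of these are algorithm-prescribed CTs. The number beyond usual care cannot be derived from the documents.

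**Primary estimate if k patients are undetermined.** Take 600 patients and 75 PE found (12.5%). Excluding the k patients rather than counting them PE-free shifts the estimate by d = 75/(600 − k) − 75/600.

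| Shift d | Solve | k needed |
|---|---|---|
| 0.5 points | 600 − 75/0.130 = 23.1 | 24 |
| 1 point | 600 − 75/0.135 = 44.4 | 45 |
| 2.5 points | 600 − 75/0.150 = 100 | 100 |

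With 90 or 60 PE found, the three thresholds are 20 or 29, 38 or 55, and 86 or 120.

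Bounds that count none or all of the k patients as PE have full width k/600, which is 1 point per 6 patients. Compared like for like with the full CI width of about 5 points, this needs k ≈ 0.05 × 600 = 30.

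**The two subgroup names.** If every indicated CT and no other is done, as Study Procedures describes, the imaged set and the indicated set are identical and the gap is zero. To see what departures would do, assume 75 PE among those indicated, 5% or 10% of them not imaged at the same PE rate, and the non-imaged counted PE-free. The indicated numbers and missing rates are assumptions.

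| Indicated | Imaged basis | Indicated basis (5% / 10%) | Gap (points) | 95% half-width (points) |
|---|---|---|---|---|
| 200 | 37.5% | 35.6% / 33.75% | 1.9 / 3.75 | 6.7 |
| 300 | 25.0% | 23.75% / 22.5% | 1.25 / 2.5 | 4.9 |
| 400 | 18.75% | 17.8% / 16.9% | 0.9 / 1.9 | 3.8 |

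For 300 indicated and 5% not imaged: 71.25/285 = 25.0% against 71.25/300 = 23.75%. Every gap lies inside the sampling error of the subgroup estimate.

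**The case for a change.** The strongest case for acting is that the contradiction is plain on the page, involves contrast imaging, and would take one sentence to remove. A usual-care reading has some support: the algorithm is guideline-based, the D-dimer assay is each centre's routine one, and the list of what the Promoter funds names no tests. It does not dissolve the conflict, because the protocol applies the algorithm to every eligible patient with recent exertional dyspnoea, not only to those in whom PE is suspected. That part of the objection stands.

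The statistical part is weaker. Read literally, the Ethics sentence could mean that work-up is left to local practice, and selective testing on a large scale would matter a great deal for a prevalence estimate. But the plan contains no analysis, endpoint definition or enrolment path for patients who skip the work-up. The endpoint is defined only through the algorithm, patients who cannot have CT are excluded, and completeness is monitored remotely. Nothing in the documents suggests a material number of undetermined patients.

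The missing rule for such patients is a real gap, though a small one. An analyst would ordinarily report how many there are and show how the estimate moves under either treatment of them.

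**Conclusion.** This is a wording inconsistency of low severity. The Ethics and Study Procedures statements must be reconciled, and this note takes no position on which account of the investigations is correct. Reconciling them changes no number: with the work-up carried out as described, every patient is classified, the two subgroup names denote the same patients, and the primary estimate and its CI are as planned.

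The 60–90 CTs are an expected floor at 600 patients and 10–15% prevalence, and say nothing about how many CTs the study causes. The choice of denominator becomes noticeable (0.5 points) only at about 4% undetermined patients, assuming 75 PE found in 600. The none/all bounds become as wide as the planned interval only at about 30 patients. The subgroup gaps rest on assumed rates and stay within sampling error. If many patients were in fact left without a work-up, the conclusion would need to be revisited, but that would be a departure from Study Procedures, not a consequence of the analysis plan.
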